### 9.3 Analysis of Primary Endpoint

Hypothesis testing based on non-inferiority of PFS rate at 20 months will be performed for each arm using an exact test for one proportion. Furthermore, PFS will be estimated using the Kaplan Meier method and estimates at 20 months, other specific time points and 95% confidence interval will be calculated. Survival analysis models such as Cox regression will also be considered.

An intent-to-treat analysis will be initially performed wherein all patients who received at least one dose of the treatment regimen is included in the analysis. For the primary endpoint of PFS at 20 months, patients who drop-out and are not evaluated for the 20 month time point will be considered non-evaluable. Subjects will be followed for up to 36 months in order to capture significant events and median PFS (secondary endpoint) estimates.

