1.2.3 To evaluate median Progression-free Survival (PFS)

1.2.4 To evaluate urinary 5- HIAA at baseline and at 12 months

1.2.5 To evaluate quality of life as measured by the QLQ-C30 and QLQ-GI.NET21, two complementary instruments developed by the European Organization for Research and Treatment of Cancer (EORTC)

1.2.6 To evaluate effect of combination of Telotristat (250mg TID VS. 500mg TID) plus Lu 177 Dotataate on carcinoid syndrome diarrhea and flushing

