## Study Design/Endpoints

This is an open label, randomized, parallel arm, Phase II trial of two dose levels of Telotristat (250 mg TID and 500 mg TID) in combination with Lutetium Lu 177 Dotataate (Lutathera). The primary endpoint of the study is 20-month PFS. The study is designed to test a non-inferiority hypothesis for one proportion (proportion of patients had 20-month progression-free) for each arm separately. No interim analysis will be performed. All patients will be followed up to 36 months after the study enrollment. An intent-to-treat analysis will be performed and patients who drop-out prior to 20 months of follow-up will be deemed non-evaluable for the primary objective and excluded from primary objective analysis. PFS distribution and median PFS will be estimated using Kaplan-Meier method based

on 36 months follow-up data.

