Radiolabeled somatostatin analogue Lutetium Lu 177 Dotataate is a beta- and gamma-emitting radionuclide. Radiolabeled somatostatin analogues provide a means of delivering targeted radiation with a high therapeutic index to tumors that express somatostatin receptors. Data from nonrandomized trials of Lutetium Lu 177 Dotataate have consistently shown high response rates and long durations of median progression-free survival in heterogeneous patient populations with gastroenteropancreatic neuroendocrine tumors. The NETTER-1 trial validates these early-phase data in the context of a prospective, randomized trial. In summary, Lutetium Lu 177 Dotataate resulted in markedly longer progression-free survival than high-dose octreotide LAR and was associated with limited acute toxic effects in a population of patients who had progressive neuroendocrine tumors that originated in the midgut.

We hypothesize that inhibition of serotonin production will lead to cytostatic effect on neuroendocrine tumors and will complement anti-tumor activity of lutetium 177 dotataate. We anticipate our proposed combination will result in improved treatment efficacy as reflected by improved 20-month PFS as compared to historical control.

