#### Available Alternative Opportunities/Treatments

Describe alternative treatments or opportunities that might be available to those who choose not to participate in the study, and which offer the subject equal or greater advantages. If applicable, this should include a discussion of the current standard of care treatment(s).

Subjects can get the usual treatment for this type of cancer without being on study. They can participate in another study, if one is available. They can receive only palliative care or refuse all treatment.

The usual approach for patients who are not in a study is treatment with Lutetium Lu 177 Dotataate or everolimus, which are both approved by the Food and Drug Administration (FDA). Everolimus is able to keep the disease stable in 50 out of 100 treated patients for about 11 months. Lutetium Lu 177 Dotataate is able to keep the disease stable in 50 out of 100 treated patients for about 30-35 months.

[Back to Top](#)

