## 9. STATISTICAL CONSIDERATIONS

### 9.1 Study Design/Endpoints

This is an open label, randomized, parallel arm, Phase II trial of two dose levels of Telotristat (250 mg TID and 500 mg TID) in combination with Lutetium Lu 177 Dotatate (Lutathera). The primary endpoint of the study is 20-month PFS. The study is designed to test a non-inferiority hypothesis for one proportion (proportion of patients had 20-month progression-free) for each arm separately. No interim analysis will be performed. All patients will be followed up to 36 months after the study enrollment. An intent-to-treat analysis will be performed and patients who drop-out prior to 20 months of follow-up will be deemed non-evaluable for the primary objective and excluded from primary objective analysis. PFS distribution and median PFS will be estimated using Kaplan-Meier method based on 36 months follow-up data.

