### 9.2 Sample Size/Accrual Rate

A sample of 33 patients per arm will provide 80% power to test a non-inferiority difference of 5% for the combination based on a one-sided test with 5% significance level. Based on the NETTER trial [7], we will assume that PFS rate at 20 months is equal to 65%. We will further assume a small non-inferiority margin of 5% and that the PFS at 20 months with the PRRT (Lutathera)+Telotristat combination is equal to 80%. The assumption in hypothesized effect size of the combination is based on the width of the 95% confidence interval presented in the NETTER trial results. If at least 25 out of 33 patients in each arm progression-free at 20 months, we will conclude that PFS rate at 20 months for the combination (either arm) is non-inferior. To account for a potential 5% drop-out/non-evaluable rate, we will enroll 35 patients per arm. We expect to enroll 2-3 patients per month. Thus, a total of 70 patients requires an accrual duration approximate of 30 months (2.5 years) and study duration approximate of 66 (5.5 years) months (30 months accrual plus 36 months follow-up)

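### Does 36 months of follow-up undermine median PFS as a secondary endpoint if the combination works as hypothesised?

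*Combined protocol and SAP*

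**What the plan says.** Objective 1.2.3 makes median PFS a secondary objective. Section 9.1 states: "PFS distribution and median PFS will be estimated using Kaplan-Meier method based on 36 months follow-up data". The Study Design/Endpoints text in the IRB application repeats this. Section 9.3 ties follow-up to the same quantity: "Subjects will be followed for up to 36 months in order to capture significant events and median PFS (secondary endpoint) estimates".

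Section 9.3 also says of the Kaplan-Meier analysis that "estimates at 20 months, other specific time points and 95% confidence interval will be calculated". The other time points are not listed, and the plan does not say how an unreached median will be reported.

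Section 9.2 takes 65% as the historical 20-month PFS rate and a 5-point non-inferiority margin. For power it assumes that "the PFS at 20 months with the PRRT (Lutathera)+Telotristat combination is equal to 80" percent. The benefits discussion in the IRB application expects improvement: "We anticipate our proposed combination will result in improved treatment efficacy as reflected by improved 20-month PFS as compared to historical control". The section on alternative treatments gives a lay figure for the control treatment: "Lutetium Lu 177 Dotataate is able to keep the disease stable in 50 out of 100 treated patients for about 30-35 months".

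**The concern.** The follow-up period and the design alternative seem to work against each other. If four in five patients are progression-free at 20 months, and progression continues at roughly the same rate, about two thirds are still progression-free at 36 months. The Kaplan-Meier curve then does not cross 50% within follow-up. Median PFS is the only PFS quantity named as a secondary endpoint, so it would usually have no point estimate and no upper limit in the case where the combination does what the investigators hope.

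The 16 months of follow-up beyond the primary time point would then be justified partly by a quantity they are unlikely to deliver. A reader might want the plan to name quantities that can always be estimated, such as the 36-month PFS rate or restricted mean PFS to 36 months. The primary test is not at stake.

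**Working it through.** **Inputs.** From sections 9.1 and 9.2: 33 evaluable and 35 enrolled patients per arm, 5% drop-out, 36 months of follow-up, historical rate 65%, null rate 65% − 5% = 60%, alternative 80%, success at 25 or more of 33. The documents give no hazard shape, so every shape below is an assumption.

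**The plan's own figure.** For X ~ Binomial(33, p), P(X ≥ 25) is 0.0444 at p = 0.60 and 0.79996 at p = 0.80. The stated 80% power at one-sided 5% is reproduced.

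**Constant hazard, 80% at 20 months.**
- Median = 20 × ln 2 / (−ln 0.80) = 62.1 months.
- S(36) = 0.80^(36/20) = 0.80^1.8 = 0.669.
- With complete follow-up, a 35-patient arm reaches its median only with at least 18 events: P(Binomial(35, 0.331) ≥ 18) = 0.019.
- Simulation with 5% drop-out by month 20 gives 0.021. The lower 95% limit of the median is reached in about 58% of arms and the upper limit in under 0.1%.

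**Range for the shape.** A Weibull curve through 65% at 20 months with a control median m has shape k = ln(ln 2 / −ln 0.65) / ln(m/20). The lay figures m = 30 and m = 35 give k = 1.17 and 0.85. If the combination keeps those shapes, its median is 52.6 or 75.9 months, and the median is reached in 4.7% or 1.0% of arms (simulation).

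**Other shapes, still 80% at 20 months.** The 1–5% range assumes that the control curve's shape carries over to the combination and that the benefit persists to month 36. The documents support neither step.
- Hazard returns to the control rate after month 20: S(36) = 0.80 × 0.65^1.8 / 0.65 = 0.80 × 0.461 / 0.65 = 0.567, and P(Binomial(35, 0.433) ≥ 18) = 0.21.
- Weibull shape 1.5: about 16%. Shape 2: about 57%.

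**Smaller effects, constant hazard, simulation with 5% drop-out.**

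| True 20-month PFS | S(36) | Arms reaching the median |
|---|---|---|
| 75% | 0.596 | 13% |
| 70% | 0.526 | 38% |
| 65% | 0.461 | 68% |

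At 65% the true median is 20 × ln 2 / (−ln 0.65) = 32.2 months, inside follow-up. Shapes 0.85 and 1.17 give 54% and 81%.

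**What the plan already delivers.** A Kaplan-Meier estimate of the PFS distribution from 36 months of data includes S(36). The 20-month rate, which is the comparison with the historical control, is both the primary endpoint and a planned Kaplan-Meier estimate with an interval.

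**The case for a change.** The strongest case for a change is that the only named secondary PFS endpoint is likely to lack a value when the treatment works. The 20-month estimate belongs to the primary endpoint and cannot stand in for it. The other time points are unlisted, so in an open-label trial they could be picked after the data are seen. Naming the 36-month rate and restricted mean PFS costs only wording, and both can be estimated at 80% (67% and 29.6 months) and at 65% (46% and 25.0 months).

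The conditional arithmetic stands, and so do two small gaps: month 36 is not named, and no sentence covers an unreached median. Neither puts a result at risk. Month 36 is the planned end of follow-up and the natural last landmark on a curve the plan already produces. Standard software prints an unreached median as such, with its lower limit where that exists. No decision rule depends on these estimates.

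The case for restricted mean PFS is weaker. No stated objective needs it, the documents give no historical value for it (25.0 months is derived from the 65% rate), and its simple 95% interval covers about 93% at this sample size.

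The complaint about the follow-up rationale also weakens on reading. The sentence states a purpose, names significant events as well as the median, and does not promise that the median will be reached. For a non-inferiority question against a control median of about 30–35 months, 36 months is a sensible horizon. A median not reached by then would itself be favourable information.

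**Conclusion.** No change follows. If 20-month PFS is truly 80%, the median is unlikely to be reached by 36 months: about 2% of 35-patient arms under constant hazard, about 21% if the hazard returns to the control rate after month 20, and up to 57% for a steep curve. If the combination only matches the historical 65%, about two thirds of arms reach it. In each case the plan as written yields the PFS curve, landmark rates with intervals and a reportable statement about the median. The primary test and the 20-month comparison are unaffected.

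What remains is detail that an analyst fills in sensibly: include month 36 among the landmark times and report an unreached median with its lower limit.

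These figures rest on the planned 35 per arm and on assumed curve shapes. The project information in the IRB application gives a maximum of 12 subjects. With 6 per arm (assumed), complete follow-up, constant hazard and 80% at 20 months, P(Binomial(6, 0.331) ≥ 3) = 0.31, so the 2% would not apply. The reason for leaving the plan alone would be the same.

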## **9.4 Analysis of Secondary and Exploratory Endpoints**

### **9.4.1 Analysis of Secondary Endpoints**

ORR will be assessed by RECIST v1.1 of CT/MRI scans completed at 6 and 12 months post-initiation of study treatment, and will be estimated along with 95% binomial confidence intervals.

Comparison of pre vs. follow-up measurements of urinary 5-HIAA and QOL will be performed using paired t-tests or linear mixed models for repeated measurements. Carcinoid syndrome assessment of diarrhea and flushing will be summarized at each time point of follow-up and paired comparisons will be performed using non-parametric Wilcoxon signed-ranks test or paired test for proportions.

Safety data for this combination will be summarized in a descriptive table. All patients who received study drugs will be included in the safety analysis. The maximum grade of toxicity for each AE category of interest will be recorded for each patient and the summary results will be tabulated by category and grade. We will describe all serious ( $\geq$  grade 3) toxicity events on a patient-by-patient basis. Frequency and incidence tables of toxicity and AEs will be generated for each treatment arm.

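### Diarrhea and flushing are to be compared only by complete-pair tests, which can show improvement where there is none if progressing or withdrawing patients stop giving symptom data

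*Combined protocol and SAP*

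**What the plan says.** Secondary objective 1.2.6 is the trial's symptom question: "To evaluate effect of combination of Telotristat (250mg TID VS. 500mg TID) plus Lu 177 Dotataate on carcinoid syndrome diarrhea and flushing".

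Section 9.4.1 (repeated in the Study Design part of the application) gives its analysis. On timing: "Carcinoid syndrome assessment of diarrhea and flushing will be summarized at each time point of follow-up and paired comparisons will be performed". On method: "paired comparisons will be performed using non-parametric Wilcoxon signed-ranks test or paired test for proportions".

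For the neighbouring outcomes the same section offers more: "Comparison of pre vs. follow-up measurements of urinary 5-HIAA and QOL will be performed using paired t-tests or linear mixed models for repeated measurements". Mixed models are not offered for diarrhea or flushing.

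The only rule for drop-outs concerns the primary endpoint. In section 9.1, "patients who drop-out prior to 20 months of follow-up will be deemed non-evaluable for the primary objective and excluded from primary objective analysis". Nothing in the supplied text says how missing symptom values are handled, whether symptoms are still recorded after progression, or which time point carries the conclusion. The visit schedule is in an attached study calendar that was not supplied.

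**The concern.** A paired test at a given visit needs a baseline value and a value at that visit. A patient who has left symptom assessment by then drops out of the comparison. Pairing does not protect against this: it removes differences in baseline level, but the missing patients may be the ones whose change was unfavourable.

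A link between worsening symptoms and tumor progression is plausible on the trial's own reasoning, since the benefits section of the application proposes that blocking serotonin production also slows tumor growth. If the link exists and progressing patients leave assessment, the remaining pairs lean towards improvement. The lean grows as more patients progress, so it could be read as a lasting symptom benefit.

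**Working it through.** **The plan's own figure.** No sample size, alpha or power is given for diarrhea or flushing. The primary design, which supplies the inputs below, reproduces. With a null of 65% − 5% = 60% and an alternative of 80%, the rule of at least 25 of 33 has exact one-sided alpha 0.0444 and power 0.79996. Inflating for 5% drop-out gives 33/0.95 = 34.7, so 35 per arm.

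**Inputs from section 9.2.** 20-month PFS of 80% (combination) and 65% (historical), 5% drop-out, 35 enrolled per arm.

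**Assumptions not in the documents.** PFS has a constant hazard. Patients give no symptom data after progression. Symptom change is standard normal with true mean 0. Worsening and progression have correlation ρ of 0.3 to 0.5, with 0 as the reference.

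**Step 1: share lost by month 12.** h = −ln S(20)/20 and loss q = 1 − exp(−12h).

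- S(20) = 0.80: h = 0.01116, q = 0.125, leaving 30.6 of 35.
- S(20) = 0.65: h = 0.02154, q = 0.228, leaving 27.0 of 35.

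**Step 2: bias in those who remain.** If progression removes the top q of a normal variable correlated ρ with worsening, the mean change among the rest is shifted towards improvement by ρ·φ(c)/(1 − q), where c is the standard normal quantile at 1 − q.

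| Loss q | φ(c)/(1 − q) | ρ = 0 | ρ = 0.3 | ρ = 0.5 |
|---|---|---|---|---|
| 0.05 (planned drop-out only) | 0.1031/0.95 = 0.109 | 0 | 0.03 SD | 0.05 SD |
| 0.125 (month 12, 80% PFS) | 0.2062/0.875 = 0.236 | 0 | 0.07 SD | 0.12 SD |
| 0.228 (month 12, 65% PFS) | 0.3020/0.772 = 0.391 | 0 | 0.12 SD | 0.20 SD |

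Simulations, one of which generated progression through a shared frailty, gave 0.06 to 0.20 SD at month 12, in agreement.

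**Step 3: false improvement.** Signed-rank test on the remaining pairs, 35 patients at the start, two-sided 5%, counting only results in the direction of improvement (nominal 2.5%). At month 12 with ρ of 0.3 to 0.5, independent simulations gave 5% to 15% and 6% to 17%. At ρ = 0 the rate was 2% to 3%. At 5% loss it was about 3% to 4%.

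**Step 4: later times, only if symptoms are collected then.** The same hazards give losses of 23.5% to 40.4% at month 24 and 33.1% to 53.9% at month 36. Over ρ of 0.3 to 0.5 the bias is 0.12 to 0.33 SD and 0.16 to 0.43 SD, and false improvement is about 7% to 33% and 11% to 39%.

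**Step 5: what a repeated-measures model gains.** In simulations of a continuous change score with loss at progression, a likelihood-based mixed model roughly halved the bias at months 24 to 36. For example, at month 36 with 65% PFS and ρ = 0.5 it fell from 0.42 to 0.20 SD. At ρ = 0 the model did no harm. Independence GEE left the complete-pair bias unchanged (0.44 SD in the run that tested it). The gain comes from visits recorded before a patient is lost, so a model with a single follow-up visit would gain nothing.

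**The case against.** The strongest reply is that the central premise is not in the documents. Nothing supplied says that symptom assessment ends at progression, and section 9.1 plans up to 36 months of follow-up for all patients, though it does not mention symptom data. This stands, and it is why the point is conditional.

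A reader might go further and infer that symptoms are tested at every visit to month 36, so that the largest figures in Step 4 apply. The text does not support that. It says symptoms are summarized at each time point and, separately, that paired comparisons are made. The long follow-up has another stated purpose: "Subjects will be followed for up to 36 months in order to capture significant events and median PFS (secondary endpoint) estimates". No supplied text schedules a symptom assessment at month 24 or 36.

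A reader might also extend the criticism to 5-HIAA and quality of life. That does not hold: mixed models are already allowed for both, and objective 1.2.4 gives 5-HIAA one follow-up ("To evaluate urinary 5- HIAA at baseline and at 12 months"), so it has no series of shrinking late comparisons.

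The size also depends on an assumed correlation, and the only loss rate the plan states is 5%, at which the bias is small. The Project Information page gives a maximum of 12 subjects against 70 in section 9.2; with 12 pooled, false improvement at month 12 would be about 3% to 5%, although the bias in SD units would not shrink. Finally, these are secondary endpoints of an open-label phase II trial whose decision rests on 20-month PFS.

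What the reply leaves untouched is that only complete-pair tests are named for these symptoms, with no missing-data rule, while a better class of method is already allowed in the same section.

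**Conclusion.** The point holds in conditional form. Section 9.4.1 limits diarrhea and flushing to complete-pair tests. If progression or withdrawal ends symptom data, those tests describe a selected group. At month 12 the bias would then be about 0.06 to 0.20 SD and the false-improvement rate about 5% to 17% against 2.5%. This rests on a constant hazard through the plan's PFS rates, complete loss at progression, 35 patients per arm, and a correlation of 0.3 to 0.5. The effect is larger if symptoms are collected and tested later, about 0.03 to 0.05 SD if only the planned 5% are lost, and near zero if worsening and progression are unrelated.

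The documents do not show that the bias will occur; they leave it open. The primary endpoint is not affected.

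**What to change.** In section 9.4.1:

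- Analyse diarrhea and flushing with a likelihood-based repeated-measures model on all available visits (an ordinal or binary generalized linear mixed model), with baseline, visit and arm. Unweighted GEE is not a substitute, because it does not deal with loss that depends on outcome.
- Name one main time point, such as month 12, provided the calendar has a symptom assessment there.
- Report the number of complete pairs and the number of patients progressed at each visit.
- Label paired results after the main time point as descriptive.
- State whether symptoms are recorded after progression. If they are, one sentence settles most of this point.

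Replacing the month-12 value by one taken at an exit visit is not advised: it mixes different times in one endpoint and adds a data collection.

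The cost is a change of SAP wording and a standard model on symptom data already planned. The model reduces the bias (by roughly half at months 24 to 36 in a simulation of a continuous score, not of the ordinal or binary model itself) but does not remove it. It may need a simpler form if few patients are enrolled, and late symptom results lose their confirmatory reading.

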#### Analysis of Secondary and Exploratory Endpoints

ORR will be assessed by RECIST v1.1 of CT/MRI scans completed at 6 and 12 months post-initiation of study treatment, and will be estimated along with 95% binomial confidence intervals.

Comparison of pre vs. follow-up measurements of urinary 5-HIAA and QOL will be performed using paired t-tests or linear mixed models for repeated measurements. Carcinoid syndrome assessment of diarrhea and flushing will be summarized at each time point of follow-up and paired comparisons will be performed using non-parametric Wilcoxon signed-ranks test or paired test for proportions. Safety data for this combination will be summarized in a descriptive table. All patients who received study drugs will be included in the safety analysis. The maximum grade of toxicity for each AE category of interest will be recorded for each patient and the summary results will be tabulated by category and grade. We will describe all serious (= grade 3) toxicity events on a patient-by-patient basis. Frequency and incidence tables of toxicity and AEs will be generated for each treatment arm.

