### Attachments

## Data Collection & Research Materials

In this section, please provide the following:

- Describe all sources or methods for obtaining research materials about or from living individuals (such as specimens, records, surveys, interviews, participant observation, etc.), and explain why this information is needed to conduct the study.
- For each source or method described, please list or attach all data to be collected (such as genetic information, interview scripts, survey tools, data collection forms for existing data, etc.).
- If you will conduct a record or chart review, list the beginning and end dates of the records you will view.

The data that will be collected is summarized in the attached Appendix Study Calendar (Research Procedures section).

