### **9.4.2 Analysis of Exploratory Endpoint**

Radiographic expression of somatostatin receptors will be summarized using descriptive statistics. Krenning Score from the gallium 68 Dotatate or copper 64 Dotatate will be summarized by calculating the proportion of patients in each Krenning Score category and exploratory assessments for association with clinical response (ORR) will be performed using Fisher's exact test. Median, interquartile range will be calculated for quantitative image measurements from gallium 68 Dotatate or copper 64 Dotatate and exploratory comparison of levels with clinical response (ORR) will be performed using two sample t-test or nonparametric analogs.

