## **9.6 Randomization and Stratification**

Permuted block randomization will be generated with a 1:1 allocation ratio for the two treatment arms. A separate randomization list will be generated to account for the stratification factor of tumor grade (Grade 1 and 2). The study statistician will generate the randomization list and incorporated into the clinical trial management system.

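### Objective 1.2.6 sets 250 mg TID against 500 mg TID for diarrhea and flushing, but section 9.4.1 plans no estimate of the randomised dose difference

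*Combined protocol and SAP*

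**What the plan says.** Objective 1.2.6 is "To evaluate effect of combination of Telotristat (250mg TID VS. 500mg TID) plus Lu 177 Dotataate on carcinoid syndrome diarrhea and flushing". Section 9.1 describes the design: "This is an open label, randomized, parallel arm, Phase II trial of two dose levels of Telotristat". Section 9.6 adds: "Permuted block randomization will be generated with a 1:1 allocation ratio for the two treatment arms".

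The analysis of these symptoms is in 9.4.1 and is repeated in the Study Design part of the IRB application: "Carcinoid syndrome assessment of diarrhea and flushing will be summarized at each time point of follow-up and paired comparisons will be performed". The methods named in the same place are all within-patient tests: "paired comparisons will be performed using non-parametric Wilcoxon signed-ranks test or paired test for proportions". Neither copy says whether the summaries and tests are done by arm or on all patients together.

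**The concern.** Patients in different arms of a parallel trial are not paired, so a paired test can only compare a patient with his or her own earlier value. That within-patient change combines telotristat, Lutathera and the passage of time. It also includes regression to the mean to the extent that patients enter when symptoms are bad; the eligibility appendix that would settle this is not shown. Randomisation removes these shared influences only when the two arms are compared with each other, and 9.4.1 does not plan that comparison.

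The trial could therefore finish with a randomised dose question in its objectives and no planned answer. A reader would have to set two before-after results side by side. A difference in significance between arms is not evidence of a difference in effect, and significance in both arms does not show that the effects are equal. With two symptoms, several visits and no effect measure fixed in advance, there is also room for selective reporting.

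**Working it through.** **1. Search for a between-arm analysis elsewhere in the plan.**
- 9.3 on the main test: "Hypothesis testing based on non-inferiority of PFS rate at 20 months will be performed for each arm using an exact test for one proportion". This is a one-sample test in each arm. Cox regression is only to be considered, and only for PFS.
- 9.4.1, urinary 5-HIAA and quality of life: paired t-tests or mixed models, for pre versus follow-up. They are not named for diarrhea or flushing.
- 9.4.1, safety: tables by arm, for toxicity and adverse events.
- 9.4.2: "exploratory comparison of levels with clinical response (ORR) will be performed using two sample t-test or nonparametric analogs". Together with Fisher's exact test for Krenning category, this relates imaging to response, not one arm to the other.

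None of these gives a dose difference for the symptoms.

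**2. The plan's own figure.** The only sample-size figure is the one in 9.2 for the primary endpoint. With a null rate of 65% − 5% = 60% and an alternative of 80%, the exact binomial gives P(X ≥ 25 | 33, 0.60) = 0.0444 and P(X ≥ 25 | 33, 0.80) = 0.79996. Allowing for 5% drop-out, 33/0.95 = 34.7, which rounds up to 35. The figure reproduces, but it is a one-sample calculation and says nothing about comparing doses.

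**3. What the named tests would show.** The documents give no effect size for the symptoms, so these cases are illustrations. Assumptions: 33 per arm, two-sided 5%, normally distributed changes with SD 1, 100,000 simulated trials.

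| Analysis | Assumed change, arm A / arm B (SD) | Result |
|---|---|---|
| Wilcoxon by arm | 0.5 / 0.5 | power 77% in each arm; verdicts differ in 35% |
| Wilcoxon by arm | 0.75 / 1.25 | both significant in 98% |
| Wilcoxon by arm | 0 / 1.0 | significant in 5% and over 99.9% |
| Wilcoxon pooled, 66 patients | 0.5 / 0.5 | power 97% |
| Wilcoxon pooled, 66 patients | 0 / 1.0 | power 95% |

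Analytic check of the first row with a paired t-test: power p = 0.795, so the verdicts differ with probability 2p(1 − p) = 2 × 0.795 × 0.205 = 0.326.

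The pooled rows look alike because the mean change is 0.5 SD in both. With changes of 0 and 1.0 only the spread grows, to √(1 + 0.25) = 1.118.

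For a yes/no symptom, take exact McNemar with 30% improving and 5% worsening in both arms (assumed). Power is 0.628 per arm, and the verdicts differ with probability 2 × 0.628 × 0.372 = 0.467.

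**4. What a between-arm estimate would deliver.** The 95% half-width, before any gain from baseline adjustment, is t(0.975, 2n − 2) × √(2/n) in SD units for means, and 1.96 × √(2p(1 − p)/n) for proportions, with p assumed between 0.3 and 0.5.

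| n per arm | Means | Proportions | Detectable with 80% power |
|---|---|---|---|
| 33 | 1.998 × 0.246 = 0.49 SD | 22 to 24 points | 0.70 SD |
| 16 (assumed number with the symptom at baseline) | 2.042 × 0.354 = 0.72 SD | 32 to 35 points | 1.02 SD |

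**The case against.** The best defence is that 1.2.6 is not really a contrast. Its grammatical object is the effect of the combination, with the doses in brackets. The trial tests each arm on its own, and no hypothesis, sample size or decision rule compares the arms. On that reading, summaries and paired tests by arm are what the objective needs. No section proposes to infer a dose difference from two p-values, and by-arm summaries would let a reader subtract one from the other. The by-arm tests also separate an extreme case, as the 0 / 1.0 SD row shows.

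Part of this stands. A by-arm reading of 9.4.1 is plausible, and a powered comparison is not implied. But the objective itself puts one dose versus the other, the plan never says the symptom summaries are by arm, and subtracting two summaries gives no pre-specified effect measure, visit or interval. If description by arm is what is meant, the objective should say so.

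A second objection is precision. The IRB application gives a maximum of 12 subjects in its project information, against 70 in the study population text and in 9.2. If 12 governs, with 6 per arm assumed, the half-width becomes 2.228 × √(2/6) = 1.29 SD, and only description is realistic. That favours rewording the objective; it does not supply the missing analysis.

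**Conclusion.** The point holds. The analysis named in 9.4.1 cannot answer the dose question in 1.2.6, whether it is run by arm or pooled, and nothing else in the plan does so. This conclusion rests on the text.

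The size of the practical harm rests on assumed effects: discordant verdicts in about 35% of trials (Wilcoxon) or 47% (McNemar) when the arms do not differ, and significance in both arms in 98% when they differ by 0.5 SD. The symptom scale, visit schedule and share of patients with symptoms at baseline are in attachments not shown, so the true size could be smaller or larger.

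This is a secondary objective in an open-label phase II trial, and the 25-of-33 rule is untouched. It should be corrected, but it does not threaten the main result.

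**What to change.** Choose one of two changes, and make it in both 9.4.1 and the matching IRB application text.

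- **Plan the contrast.** State that 1.2.6 is analysed by the between-arm difference (500 mg minus 250 mg, or an odds ratio if the measure is categorical) with a 95% confidence interval at a visit named in advance. Adjust for the baseline value and, if numbers allow, the grade stratum. Label it unpowered estimation in an open-label trial, and present the paired results by arm as descriptive.
- **Reword the objective.** If only description of each arm is intended, say so in 1.2.6, and state in 9.4.1 that summaries and paired tests are by arm.

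The cost is one or two sentences. The paired tests already need a baseline and a follow-up value per patient, which is what the contrast uses, so no extra patients or data are required. The form of the model must follow the symptom scale in the study calendar. The drawbacks are wide intervals, as worked out above, and reporting bias from open-label treatment, which no analysis removes. The conflict between 12 and 70 subjects should be resolved before choosing.
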